8.2.3 Restrictions

8.2.3.1 Restrictions regarding concomitant treatment

Concomitant medications, or therapy to provide adequate supportive care, may be given as clinically necessary.

Additional experimental immunosuppressant treatment and/or standard immunotherapy is not allowed concomitantly with the administration of study treatment.

8.2.3.2 Restrictions on diet and life style

Subjects should be advised there are no dietary or lifestyle restrictions.

8.2.3.3 Women of Child-Bearing Potential and Pregnancy Prevention

Subjects who are not of childbearing potential due to being postmenopausal (1 year without menstruation) or surgical sterilisation (oophorectomy, hysterectomy and/or tubal ligation) do not need to use contraception to be eligible for the trial.

All other subjects are considered to have childbearing potential and must use adequate contraception throughout the trial (from screening until end of trial participation).

Acceptable methods of contraception include surgical sterilisation and double barrier method, and must be in accordance with local regulations where applicable. Double barrier method of contraception is defined as two barrier methods used simultaneously each time the subject has intercourse. Accepted barrier methods include diaphragm, female condom, cervical cap, male condom and intrauterine device (IUD) (the diaphragm and cervical cap must be used in conjunction with spermicidal jelly/cream). Those using hormonal contraceptives, or with partners using hormonal contraceptives, must also be using an

HIC#: 1603017415 Protocol version 11.0

additional approved method of contraception (as described above). Partner vasectomy, natural "rhythm" and spermicidal jelly/cream are not acceptable methods of contraception.

Women who become pregnant while participating in the study may not receive any additional doses of the HPV vaccine. The pregnancy must be reported following procedures detailed in section 12.10.2.

8.3 Vaccine compliance

The vaccine will be administered in accordance with the protocol and the instructions of a site investigator. The 9-valent HPV vaccine will be administered in the clinic by a clinic or study nurse based on study protocol.

The investigator can withdraw a subject from the study in the event of serious and persistent non-compliance with receiving the vaccine dose(s) which jeopardizes the subject's safety or render study results for this subject unacceptable.

9.0 STUDY PARAMETERS

9.1 Observations and Tests

The following observations and tests are to be performed and recorded before, during, and after treatment:

	Pre-Treatment	Treatment Period	Post-Treatment Period	End of Treatment	3 and 6 Month Post End of Treatment
Study week		8	16	22	
Study Procedures Window (weeks)	-10	± 1	+ 2	± 2	± 2
History, PE w/ pelvic exam	X	X	X	X	
Vital signs	X	X	X	X	
Urine pregnancy test	X**	X	X	X	
Pap				X	
High risk HPV test	X***			X	X
HPV 16/18 genotype	X		X	X	
Cytobrush collection*	X	X	X	X	
Colposcopy, cervical biopsy	X	X (biopsy if clinically indicated)	X (biopsy if clinically indicated)	X	
Peripheral blood sample collection*^	X****	X	X	X	
Toxicity assessment	X	X	X	X	
Randomization	X****				

- * For translational studies. Translational blood may be drawn after randomization but must be drawn prior to treatment.
- ^ See Section 6.2.1 for collection information.
- ** Urine pregnancy test must be performed within 7 days of treatment
- *** If high-risk HPV DNA results are already available, this testing may not have to be repeated
- **** Week 22 visit will occur at least 3 weeks after last dose of therapy
- ***** Randomization to occur following confirmation of eligibility

HIC#: 1603017415 Protocol version 11.0

10.0 EVALUATION CRITERIA

10.1 Objective Response

The major parameters of response to be assessed include treatment efficacy defined as histologic regression of cervical dysplasia to CIN 1 or less 12 to 16 weeks after the end of imiquimod treatment, HPV clearance and treatment tolerance.

- 10.11 Histologic regression: Only subjects with histologically confirmed CIN 2,3 as reviewed by a central study pathologist will be enrolled in the study. All index biopsy sites noted to have CIN 2,3 at baseline must be assessed via colposcopy. Cervical biopsy at the final colposcopy will be collected from the worst areas of residual disease. Included in the evaluations are the following criteria:
 - Histologic regression (HR): Histologic regression of all index lesions to CIN 1 or less at 12 to 16 weeks after end of imiquimod treatment period.
 - Histologic remission (HM): Complete regression of cervical dysplasia at all index biopsy sites at 12 to 16 weeks after end of imiquimod treatment period.
 - Persistent Disease (PR): One or more index lesions persists with CIN 2,3 high grade dysplasia or new lesions are identified colposcopically and histologically confirmed to be CIN 2,3.
 - Progressive Disease (PD): Worsening histology of an index lesion.
- 10.12 HPV Clearance: HPV clearance will be measured by both the Roche cobas HPV Test utilized by pathology concomitant with the pap test at final study visit which assesses for presence of 14 high risk HPV types as well as HPV 16/18 genotyping performed by [name] Lab.
- 10.13 Treatment Tolerance: The grade level of the various toxicities will be classified using the Common Toxicity Criteria, version 4 (CTC, v.4) guidelines. Acute toxicities will be scored if occurring </= 30 days from treatment completion, and chronic if > 30 days. Frequency and duration of treatment interruptions due to the treatment toxicity will be assessed.

11.0 **DURATION OF STUDY**

11.1 This study will continue as long as treatment protocols remain activated.

HIC#: 1603017415 Protocol version 11.0

CIN 2/3

11.2 The subject will be followed with routine clinical care with a 6 month colposcopy and cytology if histologic remission or regression noted at final study visit and in 12 months if cytology remains negative with normal colposcopy. Any abnormal cytology or colposcopy at 6 months should prompt cervical biopsy and management per guidelines of American Society for Colpsocpy and Cervical Pathology (ASCCP).

Those subjects with persistent CIN 2,3 or progression of disease at end of study period will be offered surgical excisional procedure per routine clinical care and should be followed by ASCCP guidelines.

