1.1 Primary objectives

- 1.1.1 To determine treatment efficacy defined as histologic regression to CIN 1 or less at weeks 20-24 (4 to 8 weeks after the end of imiquimod treatment) in the HPV Vaccine + Imiquimod group compared to control
- 1.1.2 To determine treatment efficacy defined as histologic regression to CIN 1 or less at weeks 20-24 (4 to 8 weeks after the end of imiquimod treatment) in the Imiquimod group compared to control

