15.5 Analysis for the Primary Objective

The co-primary objectives of this study are to test superior treatment efficacy of Imiquimod + HPV vaccine (Trt1) compared to control (Trt0), and likewise Imiquimod only (Trt2) compared to control (Trt0). The primary outcome is *histologic regression* (yes/no) after completion of the 12 to 16 weeks imiquimod course. The full definition of *histologic regression* and how it is determined is described in Section 5.1.

The co-primary hypothesis tests are:

 $\{H_{01}: p_1 - p_0 = 0 \text{ versus } H_{11}: p_1 - p_0 > 0\}$ and

 $\{H_{02}: p_2 - p_0 = 0 \text{ versus } H_{12}: p_2 - p_0 > 0\}$

 p_0 , p_1 , and p_2 are the proportion of subjects on Trt0, Trt1, and Trt2, respectively, who are determined to have *histologically regressed*. Fisher's Exact Test will be used to assess if the data support rejecting the null hypothesis H_{01} , and likewise for H_{02} . To control Type I error, we will use a conservative Bonferroni adjustment for multiple comparisons with one-sided $\alpha = (0.05)/2 = 0.025$ as the significance level for each test. Rejection of a particular null hypothesis suggests superior efficacy of that specific treatment compared to control. Exact 95% confidence intervals will be calculated for p_1 - p_0 and for p_2 - p_0 . Confidence intervals for 'risk ratios' (p_1/p_0 , p_2/p_0) in addition to 'risk differences' (p_1 - p_0 , p_2 - p_0) may also be estimated. The main analysis will use the **modified ITT analysis set**. Sensitivity analyses for the same statistical method using the **modified ITT completers** and/or **per protocol analysis sets** may also be provided.

HIC#: 1603017415 Protocol version 11.0

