15.8 Sample Size Justification

Anticipated annual accrual is approximately 40-45 subjects.

Our general philosophy regarding Phase II trials of new drug combinations is to facilitate the prompt discovery of inactive agents, yet allow for a reasonable estimate of the response rates for those regimens demonstrating some degree of activity. However, excessive accrual to inactive study regimens to document precise response rates is to be avoided. The purpose of this study is to evaluate the activity and potential toxicity of the combination therapy of Imiquimod + HPV vaccine in subjects with untreated high-grade CIN 2,3 cervical dysplasia. This study will implement a 3 arm randomized trial design that will allow us to estimate the treatment effect of Imiquimod + HPV vaccine compared to observation as well as Imiquimod alone compared to observation.

Based on published literature for the primary outcome,³⁸ we assume a 28% spontaneous histological regression rate in CIN 2-3 lesions with observation alone (control group). From Grimm et al.'s efficacy

HIC#: 1603017415 Protocol version 11.0

trial of imiquimod for treatment of CIN 2-3, we would like to have sufficient power to detect a 35% absolute increase in rate of histologic regression in the imiquimod only arm compared to control. Based on this data, we consider a conservative effect size estimate also of an absolute 35% higher rate of histologic regression in the imiquimod + HPV vaccine intervention arm compared with the control arm. We therefore aim to recruit a total sample size of 114 subjects (38 in each arm). Calculations based on Fisher's Exact Test indicate we will have $\geq 90\%$ power to detect a treatment effect of $\geq 29\%$ in both treatment arms independently compared to the observation arm ($\alpha = 0.025$ for each comparison to control). In addition, with n = 38 subjects per arm, we would have 80% power to detect a treatment effect size of $\geq 25\%$ in one treatment arm compared to placebo (while maintaining 90% power to detect the treatment effect size of $\geq 25\%$ in the other arm). Assuming a subject dropout rate of 20%, a total sample size of 138 (n = 46 per arm) subjects is calculated which will be recruited over 5 years.

Some operating characteristics of the study design are as follows:

Exact Operating Characteristics for the Treatment Effect Size Δ given control group rate=0.28, n=38 subjects per arm, one-sided α

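### Section 10.11 lets a woman whose index lesions have regressed but who has a new confirmed CIN 2,3 lesion meet both the regression and the persistent-disease definitions, so her status on the yes/no primary outcome is contradictory

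*Combined protocol and SAP*

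**What the plan says.** Section 10.11 sets out four response categories. Three matter here.

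- Regression, the primary outcome: "Histologic regression of all index lesions to CIN 1 or less at 12 to 16 weeks after end of imiquimod treatment period". New lesions are not mentioned.
- Remission, a secondary outcome: "Complete regression of cervical dysplasia at all index biopsy sites". This too is confined to index sites.
- Persistent disease has two limbs joined by 'or'. Either an index lesion is still CIN 2,3, or "new lesions are identified colposcopically and histologically confirmed to be CIN 2,3". The second limb is met whatever the index lesions show.

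On sampling, 10.11 requires that every index site "noted to have CIN 2,3 at baseline must be assessed via colposcopy". It adds: "Cervical biopsy at the final colposcopy will be collected from the worst areas of residual disease".

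The objective in 1.1 is worded per woman and names neither index nor new lesions: "To determine treatment efficacy defined as histologic regression to CIN 1 or less at weeks 20-24". Section 15.5 makes the outcome yes/no, compares proportions of subjects, and says that the full definition "and how it is determined is described in Section 5.1". Section 5.1 covers biopsy collection and blinded central review and contains no responder rule.

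**The concern.** The primary outcome needs exactly one value per woman. For a woman with regressed index lesions and a new confirmed CIN 2,3 lesion, 10.11 supplies two. Under the regression definition she is a yes. Under the persistent-disease definition she belongs in a category that a yes/no outcome can only treat as a no. Nothing says which prevails, so two analysts following the plan could code her differently, possibly after seeing the results.

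The more troubling coding is the one that the regression rule gives when applied literally: a woman with confirmed high-grade disease at the final visit is counted as a treatment success. Her follow-up is also described in two ways. Section 11.2 places women with regression in routine follow-up, while 6.2.2 and the closing paragraph of Section 11 direct persistent CIN 2-3 to excision. Those passages need to be reconciled with one another; this point takes no position on management.

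**Working it through.** **Step 1: set the definitions side by side.** The woman in question has every index lesion at CIN 1 or less and one new lesion confirmed as CIN 2,3.

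| Rule | Condition | Met? |
|---|---|---|
| Regression (10.11) | all index lesions CIN 1 or less | yes |
| Remission (10.11) | no dysplasia at any index site | yes, if the index sites have cleared fully |
| Persistent disease, limb 1 | an index lesion still CIN 2,3 | no |
| Persistent disease, limb 2 | a new confirmed CIN 2,3 lesion | yes |
| Objective (1.1) | regression to CIN 1 or less | not settled; lesions not specified |
| 15.5 via 5.1 | full definition said to be there | no rule found |

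The overlap follows from the words. No precedence rule appears elsewhere in the document.

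**Step 2: reproduce the plan's own figure.** Inputs from 15.5 and 15.8: control rate 0.28 ("we assume a 28% spontaneous histological regression rate in CIN 2-3 lesions with observation alone (control group"), effect +0.35 (so 0.63 on active treatment), 38 per arm, Fisher's exact test, one-sided 0.025 per comparison. Power is the sum, over all pairs (x, y) with one-sided Fisher p at or below 0.025, of Bin(x; 38, 0.63) × Bin(y; 38, 0.28). The result is 0.8269, which matches the 15.8 table.

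**Step 3: weight of one woman.** 1/38 = 0.026, or 2.6 points on an arm's rate.

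**Step 4: can one woman decide the test?** The control arm at the planning rate has 0.28 × 38 = 10.6, taken as 11 regressors.

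- 21/38 against 11/38: one-sided Fisher p = 0.018, below 0.025.
- 20/38 against 11/38: one-sided Fisher p = 0.031, above 0.025.

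Moving one woman from yes to no reverses the conclusion in that case. This is a chosen borderline case. At the planned effect (0.63 × 38 = 23.9, taken as 24, against 11) p = 0.003, and one woman would not matter.

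**Step 5: what counting her as a failure could do to power.** The documents give no frequency of new lesions. Assume that a share q of index regressors also has a new confirmed CIN 2,3 lesion. Assume also that the planning rates describe index-only regression. Each rate is then multiplied by (1 − q).

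| q (assumed) | Control | Active | Power, q in both arms |
|---|---|---|---|
| 0 | 0.280 | 0.630 | 0.827 |
| 5% | 0.266 | 0.599 | 0.785 |
| 10% | 0.252 | 0.567 | 0.740 |
| 20% | 0.224 | 0.504 | 0.650 |

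At q = 10%, about 38 × 0.63 × 0.10 = 2.4 women in an active arm and 38 × 0.28 × 0.10 = 1.1 in control change status. If q = 10% held in one arm only, power would be 0.644 (active arm) or 0.889 (control arm).

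**The case against.** The strongest reply is that the intended reading is clear enough. The opening of 10.1 and the objective in 1.1 both speak of regression to CIN 1 or less without limiting it to index lesions, 15.5 analyses subjects, and the new-lesion limb serves little purpose unless it overrides index regression. On that view only an explicit order is missing. This is a fair account of what was probably meant, and it supports the fix below. It does not remove the conflict, because the operative definition in 10.11 says index lesions and nothing gives the other limb priority.

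A reader might go further and infer that the biopsy rule produces the double status. It does not. The overlap comes from the two definitions alone, and the text never says that only the worst areas may be biopsied. Sampling the worst residual areas fits a per-woman outcome of CIN 1 or less. What the rule leaves open is narrower: how an index site that looks normal and is not biopsied should be scored.

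A reader might also infer bias in favour of active treatment. The documents do not show this. The definition applies to all arms, the pathologists are blinded to assignment, and the frequency of new lesions by arm is unknown.

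Finally, an index-lesion endpoint would be a legitimate choice. The difficulty is that 10.11 combines one with a persistent-disease category that contradicts it.

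**Conclusion.** The point holds as a contradiction between two stated rules for the primary outcome, with the same overlap for remission. The plan does not instruct anyone to score women with high-grade disease as successes; it leaves that scoring open, and the regression rule read literally gives it.

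The size per woman is certain: 2.6 points at 38 per arm. The total is not, since no frequency is given. The borderline reversal and the power figures are illustrations. The power figures rest on an assumed q and on planning rates that used the index-only definition. Which definition lies behind the 28% and the 35-point effect cannot be told from the documents. If those figures already count any CIN 2,3 as failure, the clarification costs no power relative to the plan.

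The change should be made, because the endpoint is primary and the remedy is a matter of wording. The timing phrase in the regression definition also conflicts with the 4 to 8 weeks after treatment in 1.1 and 5.1; that is a separate matter to reconcile.

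**What to change.** Amend 10.11 and 15.5 as follows.

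1. Define the outcome per woman. Regression means that the worst centrally read histology from any site biopsied at the final visit is CIN 1 or less. Any confirmed CIN 2,3 or worse, at an index or a new site, is non-regression.
2. Apply the same new-lesion rule to remission and keep remission nested within regression. Only regression versus persistent or progressive disease should be mutually exclusive. Making all four categories exclusive would wrongly take complete remitters out of the primary success count.
3. State that index sites normal on colposcopy and not biopsied do not count against regression.
4. Point 15.5 to 10.11 instead of 5.1.

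The cost is protocol and SAP wording, with no extra biopsies. The downside is that observed regression rates may be somewhat lower than under an index-only count, with some loss of power as illustrated above. The sponsor, who has the cited sources, should check which definition the planning rates used.

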3.0 SUBJECT ELIGIBILITY AND EXCLUSIONS

3.1 Eligible Subjects:

HIC#: 1603017415 Protocol version 11.0

- 3.1.1 Subjects must have untreated cervical biopsy-proven, CIN 2/3 ectocervical lesion(s).
- 3.1.2 Subjects must have satisfactory colposcopy with visualization of the entire transformation zone or a negative endocervical curettage if colposcopy is unsatisfactory.
- 3.1.3 Subjects must be high-risk HPV+ as determined by commercially available DNA hybridization test which tests for 13 high-risk HPV types.
- 3.1.4 All Subjects must have a histologic diagnosis of CIN 2,3 cervical lesion(s) confirmed by a study pathologist.
- 3.1.5 Subjects must have signed an approved informed consent.
- 3.1.6 Subjects of childbearing potential must have a negative urine pregnancy test within 7 days prior to the study entry and be practicing an effective form of contraception.
- 3.1.7 Subjects must be at least 18 years of age based on previous and current cervical cancer screening guidelines.
- 3.1.8 Subjects must be fluent in speaking English or Spanish.
- 3.2 Ineligible Subjects:
- 3.2.1 Subjects with unsatisfactory colposcopy* (unable to visualize entire transformation zone) or evidence of endocervical disease defined as CIN 2/3 diagnosed on endocervical curettage. *Subjects with unsatisfactory colposcopy but negative endocervical curettage are eligible (see 3.1.2).
- 3.2.2 Subjects with a history of invasive cervical cancer
- 3.2.3 Subjects with a history of other invasive malignancies, with the exception of non-melanoma skin cancers are excluded if there is any evidence of other malignancy being present within the last five years. Subjects are also excluded if their previous cancer treatment contraindicates this protocol therapy.
- 3.2.4 Subjects with any unstable medical issue (including cardiac issues as above, active treatment for pulmonary embolism, CVA, renal or hepatic insufficiency, active infection/sepsis requiring IV antibiotics).
- 3.2.5 Subjects who have an uncontrolled seizure disorder, or active neurological disease.

HIC#: 1603017415 Protocol version 11.0

- 3.2.6 Subjects known to be seropositive for HIV and active hepatitis, even if liver function studies are in the normal range. Subjects otherwise immunocompromised will also be excluded (chronic steroid use, taking immunosuppressive medications).
- 3.2.7 Pregnant or breastfeeding subjects.

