At approximately 3 months and 6 months after the last study visit, as per standard of care, it is recommended that subjects will have a pap smear with high-risk HPV testing. The results of this testing will be recorded in the subject's study record.

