12.0 STUDY MONITORING AND REPORTING PROCEDURES

12.1 Personnel responsible for the safety review and its frequency:

The principal investigator will be responsible for monitoring the data, assuring protocol compliance, and conducting the safety reviews at the specified frequency which must be conducted at a minimum of every 6 months (including when re-approval of the protocol is sought). During the review process, the principal investigator will evaluate whether the study should continue unchanged, require modification/amendment, or close to enrollment. Either the principal investigator, the IRB or the Yale Cancer Center Data and Safety Monitoring Committee (DSMC) have the authority to stop or suspend the study or require modifications.

12.2 The risks associated with the current study are deemed moderate for the following reasons:

- 1. The risk of progression of CIN 2,3 to invasive cervical cancer over 6-8 months from time of initial diagnosis is low and observation of CIN 2 diagnosed in young women for up to 12 to 24 months is already recommended by the ASCCP.
- 2. The risks associated with the FDA-approved drugs imiquimod and 9-valent HPV vaccine are minimal.

Although we have assessed the proposed study as one of moderate risk, the potential exists for anticipated and/or unanticipated adverse events, serious or otherwise, to occur since it is not possible to predict with certainty the absolute risk in any given individual or in advance of first-hand experience with the proposed study methods. Therefore, we provide a plan for monitoring the data and safety of the proposed study as follows:

12.3 Attribution of Adverse Events:

Adverse events will be monitored for each subject participating in the study and attributed to the study procedures / design by the principal investigator [name], according to the following categories:

a.) Definite: Adverse event is clearly related to investigational procedures(s)/agent(s).

HIC#: 1603017415 Protocol version 11.0

CIN 2/3 26

- b.) Probable: Adverse event is likely related to investigational procedures(s)/agent(s).
- c.) Possible: Adverse event may be related to investigational procedures(s)/agent(s).
- d.) Unlikely: Adverse event is likely not to be related to the investigational procedures(s)/agent(s).
- e.) Unrelated: Adverse event is clearly not related to investigational procedures(s)/agent(s).

12.4 Plan for Grading Adverse Events:

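### The primary analysis pools CIN 2 and CIN 3 at entry and never uses baseline grade, although response is a one-grade change for one group and a two-grade change for the other

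*Combined protocol and SAP*

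**What the plan says.** Entry pools the two grades. Section 3.1.4 states: "All Subjects must have a histologic diagnosis of CIN 2,3 cervical lesion(s) confirmed by a study pathologist". Section 10.11 adds: "Only subjects with histologically confirmed CIN 2,3 as reviewed by a central study pathologist will be enrolled in the study".

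Response has one threshold for everyone. Section 10.11 defines histologic regression as "Histologic regression of all index lesions to CIN 1 or less at 12 to 16 weeks after end of imiquimod treatment period", with no minimum change from the baseline grade. (The timing in that definition differs from the 4 to 8 weeks after treatment in Section 1.1. The two must be reconciled, but that is a separate matter.) All index sites "must be assessed via colposcopy", final biopsies are taken from the worst residual areas, and a new lesion confirmed as CIN 2,3 counts as persistent disease. Sections 5.1 and 6.2 provide for central reading by pathologists blinded to assignment.

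Section 6.2 describes randomization to three arms and names no stratification factor. For the primary comparisons, Section 15.5 says that Fisher's "Exact Test will be used to assess if the data support rejecting the null hypothesis". The sensitivity analyses there change the analysis set only. Section 15.4 tests baseline characteristics for homogeneity across arms. It does not name CIN grade and attaches no action to an imbalance.

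Two places suggest that grade matters and can be known. Section 12.2 justifies the risk level partly because "observation of CIN 2 diagnosed in young women for up to 12 to 24 months is already recommended by the ASCCP". Section 10.11 defines progressive disease as "Worsening histology of an index lesion".

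**The concern.** The distance to response differs by baseline grade: CIN 2 to CIN 1 is one step, CIN 3 to CIN 1 is two. If women with CIN 2 regress more often without treatment, baseline grade explains part of the variation in the primary outcome, and an unstratified test leaves that part in the noise. Two things follow.

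First, power is given up that a stratified test would recover. Second, with 38 women per arm the CIN 2 share can differ between arms by chance. The observed difference then moves for a reason unrelated to treatment, and the plan has no pre-specified way to allow for it. Adjusting only after an imbalance is seen would be open to challenge.

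The plan also does not report regression by grade, so the result would not show directly whether an effect is present in CIN 3 as well as in CIN 2.

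**Working it through.** **Inputs from Sections 15.5 and 15.8.** Control rate 0.28; difference 0.35, so 0.63 on treatment; 38 evaluable per arm; Fisher's exact test at one-sided 0.025 for each comparison with control.

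**Assumed inputs (not in the documents).** CIN 2 share s = 0.5. Control regression by grade (CIN 2/CIN 3): 40%/16%, 45%/11%, or 28%/28%. Each pair averages 28%, for example 0.5 × 40% + 0.5 × 16% = 28%. The effect is +35 points in both grades.

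**1. Reproduce the plan.** Enumerating both binomials with n = 38 and rejecting when the one-sided hypergeometric tail is at most 0.025 gives power 0.8269 at a difference of 0.35 and size 0.0147 at zero. Both match the table in Section 15.8.

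**2. Chance imbalance in CIN 2 share.** The SD of the between-arm difference in share is √(2 × 0.5 × 0.5 / 38) = 0.115, so the 95% range is ±1.96 × 0.115 = ±0.225. The resulting shift in the risk difference is the share difference times the gap between grades.

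- Gap 24 points (40%/16%): SD 0.115 × 24 = 2.8 points, 95% range ±5.4.
- Gap 34 points (45%/11%): SD 0.115 × 34 = 3.9 points, 95% range ±7.7.

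For scale, the standard error of the difference is √(0.28 × 0.72/38 + 0.63 × 0.37/38) = 10.7 points. The 2.8-point component is about (2.8/10.7)² = 7% of that variance.

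**3. Type I error, overall and given an imbalance.** Averaged over randomization, Fisher's size stays at 0.0147 even with a 40-point gap. Conditional on 23 against 15 women with CIN 2 out of 38 per arm, its false-positive rate is:

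| Gap between grades | More CIN 2 on treatment | More CIN 2 on control |
|---|---|---|
| 20 points | 0.035 | 0.004 |
| 30 points | 0.048 | 0.002 |
| 40 points | 0.064 | <0.001 |

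A difference of 8 or more women in either direction occurs in about 8% of pairwise comparisons.

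**4. Power, Fisher against an exact conditional test stratified by grade.** The stratified test sums treated responders over the two grade strata and refers the sum to the convolution of the two hypergeometric distributions. By simulation at 38 per arm, one-sided 0.025:

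| Control CIN 2/CIN 3 | Fisher | Stratified exact | Change, points |
|---|---|---|---|
| 40%/16% | 0.827 | 0.850 | +2.3 |
| 45%/11% | 0.833 | 0.880 | +4.7 |
| 28%/28% | 0.827 | 0.823 | −0.4 |

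Repeat simulations agree to within about half a point and put the loss in the last row at 0.3 to 0.4. Null size of the stratified test is 0.012 to 0.014. Both tests are exact and conservative, so the gain does not come from replacing an exact test with an asymptotic one.

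**The case against.** The strongest case against is that nothing here is invalid. Chance imbalance is already part of the sampling error, it is about 7% of the variance in the milder scenario, type I error is kept, and the gain is a few points of power under rates the documents do not give. All of that stands, and it is why the point concerns efficiency and interpretation rather than bias.

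It can also be said that the documents never state that CIN 2 and CIN 3 are recorded separately. That stands in part. Entry is written throughout as a combined category, and worsening of an index lesion could be scored as a move to invasive disease. Central review of the index biopsies can supply the grade, but the plan should say that it does.

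A reader might infer several stronger things that the documents do not support:

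- **That response rests on one biopsy, or that entry is unconfirmed.** Response requires all index lesions at CIN 1 or less, worst-area sampling, and no new CIN 2,3. Entry is centrally confirmed.
- **That a known share of control responders is misreading.** The documents give no misreading rate, and any such noise may already sit inside the planning rates of 28% and 63%.
- **That noise favours one arm.** Blinded reading and randomization make it dilution, not bias.
- **That nothing separates shallow from deep regression.** Remission is a stricter secondary outcome (Sections 1.2.1, 10.11 and 15.6), which a change from CIN 2 to CIN 1 does not meet. It is not reported by baseline grade either.
- **That follow-up results could confirm regression.** After the last visit "it is recommended that subjects will have a pap smear with high-risk HPV testing", at about 3 and 6 months. That is only a recommendation, and neither test gives a CIN grade.

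**Conclusion.** The point holds as a matter of efficiency and pre-specification. The plan pools two groups that stand at different distances from the response threshold, and it uses baseline grade neither in the randomization it describes nor in the primary analysis. Overall type I error is kept at about 0.013 to 0.015, and there is no systematic bias.

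If half the women have CIN 2 and the control rates by grade differ by 24 to 34 points, ignoring grade costs about 2 to 5 points of power (about 83% against 85% to 88%). It also leaves each comparison open to a chance shift with an SD of about 3 to 4 points. If grade is unrelated to regression, stratifying loses 0.3 to 0.4 points.

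The CIN 2 share and the rates by grade are assumptions. That grade is prognostic is likely from the way Section 12.2 treats CIN 2, but no figure in the documents shows it. The change is worth making and cheap; the trial remains valid without it.

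**What to change.** In Section 15.5, pre-specify that both primary comparisons are stratified by centrally reviewed baseline grade (worst index lesion CIN 2 versus CIN 3). Use the exact conditional stratified test at the same one-sided 0.025, with a grade-stratified risk difference and its confidence interval. In Sections 15.5 and 15.6, report regression and remission by baseline grade for each arm. In Section 5.1, state that central review records CIN 2 versus CIN 3 for each index lesion, if the two are not already held separately.

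The cost is SAP wording, minor programming and possibly one extra data field, with a power loss of 0.3 to 0.4 points if grade proves unrelated to regression. The change should be fixed before unblinded outcome data are seen. Stratifying does not reduce reading or sampling error and should not be presented as doing so.
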